5 SAMPLE SIZE CALCULATIONS

The study sample size is using a confidence interval approach to estimate precision around the true proportion of successful completion of LipiFlow treatment with Activator LFD-2100. Assuming the proportion of successful completion of LipiFlow treatment is 95%, with n=50 eyes, a two-sided 95% confidence interval will be (89%, 100%), i.e., a precision of 6.0%.

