4. STUDY DESIGN

Minimum 50 eyes and up to 100 eyes will be treated in this prospective, open-label clinical study. The investigator or designee will perform LipiFlow treatment with the Activators LFD-2100 on both eyes of a subject. The data from the treatment reports generated by the LipiFlow console and from the questionnaire will be used to assess the clinical utilization of the Activator LFD-2100.

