10.4 ACTIVATOR SUPPLY

For all the study subjects, the Activators will be obtained from the site study consignment supplied by JJSV prior to the first study treatment. One Activator will be used on each eye of a subject. Unused back-up Activators are to be returned to the site consignment. At the completion of all study treatments, any remaining Activators will be shipped back to JJSV following the final accountability by a JJSV Study Monitor. At all times, the storage, access and use of all the consignment Activators must be controlled.

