20.2 STUDY ENDPOINTS

Primary Endpoint:

- Successful completion of LipiFlow treatment with Activator LFD-2100 in 95% or more cases.

The treatment reports automatically generated by LipiFlow Console after completion of each treatment will show if the treatment completion is successful. The frequency and proportion of successful completion of treatment will be reported. The expected proportion of successful completion of LipiFlow treatment question will be greater than or equal to 95%.

Other Endpoints:

- Questionnaire rating of each step in the LipiFlow treatment procedure with Activator LFD-2100.

For questions with a 'Yes' or 'No' response, the frequency and proportion of each question with response 'Yes' will be reported. For questions with five levels of

rating score responses, the frequency and proportion of each level of rating score responses will be tabulated. The mean and median of rating score of each question will also be reported.

- Rate of adverse events and complications.

The type and rates of adverse events will be summarized.

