20.3 SAMPLE SIZE CALCULATIONS

The confidence interval approach is used to estimate precision around the true proportion of successful completion of LipiFlow treatment with Activator LFD-2100. Assuming the proportion of successful completion of LipiFlow treatment is 95%, with n= 50 eyes, a two-sided 95% confidence interval will be (89%, 100%), i.e., a precision of 6.0%.

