1 INTRODUCTION

This document summarizes the statistical methods to be implemented during the analysis of data for the evaluation of the clinical use of the LipiFlow system with Activator LFD-2100. This is a prospective, open-label clinical study. The study will be conducted at up to 4 sites with minimum 50 eyes and up to 100 eyes to be treated. Each subject will undergo 1-2 visits which include informed consent, screening for study participation, and receiving the LipiFlow treatment.

The primary endpoint is successful completion of LipiFlow treatment with Activator LFD-2100 in at least 95% cases. Additional endpoints include rating of each step in the LipiFlow treatment procedure with Activator LFD-2100, rate of complications and adverse events.

Table listings are included in Appendix I.

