2.2 DATA CONVENTIONS

Descriptive statistics will typically include sample size (N), mean, standard deviation (SD), median, minimum (Min.), and maximum (Max.) as appropriate for continuous variables. For categorical data, the frequency and proportion will be computed.

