APPENDIX I: TABLE LISTING

Variable	Subjects/Eyes
ENROLLMENT/PRE-TREATMENT	
Accountability/Enrollment	
Subjects by investigational site (n)	subjects
Demographics	
Demographic – Age in years (N, Mean, SD, Median, Min, Max), sex, race and ethnicity (n and %)	subjects
PRIMARY STUDY ENDPOINT	
Successful completion of LipiFlow treatment – (n, %) List of eyes with unsuccessful cases will be provided	eyes
OTHER ENDPOINTS	
Questionnaire responses of each step of LipiFlow treatment (n, %) for Yes/No or rating responses and mean and median for each rating score List of eyes with rating score of 1 or 2	eyes
Ocular surface staining at pre-treatment and treatment and the difference (N, Mean, SD, Median, Min, Max)	eyes
Meibomian glands assessment Meibomian glands secretion score at pre-treatment (if available) –(N, Mean, SD, Median, Min, Max) Proportion of utilization of meibomian gland evaluator (n,%)	eyes
Medical findings from slit lamp exam (n, %)	eyes
Ocular symptoms (n, %)	eyes
Rate of complications and adverse events (n, %)	eyes

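### The stated precision for 50 eyes, (89%, 100%) or 6.0%, is an unnamed Wald interval cut at 100% that takes fellow eyes as independent; its lower limit is about 4 points too favourable

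*SAP*

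**What the plan says.** SAP 5 assumes a 95% success rate and states that "with n=50 eyes, a two-sided 95% confidence interval will be (89%, 100%), i.e., a precision of 6.0" per cent. Protocol 20.3 and the sample-size paragraph of the synopsis (Protocol 1) give the same result: "a two-sided 95% confidence interval will be (89%, 100%), i.e., a precision of 6.0" per cent. All three describe the approach only as one based on a confidence interval. None names the method or says that the upper limit was truncated. No other basis for the sample size is given.

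On the unit of observation, Protocol 4 says "The investigator or designee will perform LipiFlow treatment with the Activators LFD-2100 on both eyes of a subject", and Protocol 10.4 adds "One Activator will be used on each eye of a subject". The range of sizes is in SAP 1: "The study will be conducted at up to 4 sites with minimum 50 eyes and up to 100 eyes to be treated". Neither document mentions correlation between fellow eyes.

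On the planned output, Protocol 20.2 says "The frequency and proportion of successful completion of treatment will be reported", and SAP 2.2 says "For categorical data, the frequency and proportion will be computed". SAP Appendix I tabulates the primary endpoint by eye as a count and percentage and adds "List of eyes with unsuccessful cases will be provided". No interval is listed for it.

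**The concern.** Two features of the sentence invite a check. First, an interval centred at 95% with a precision of 6.0 points cannot end at 100%, because the upper arm is then only 5 points. This suggests a symmetric normal approximation that ran past 100%, and that approximation is known to behave poorly for proportions near 1. Second, n is counted in eyes although every subject contributes two.

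What is at stake is how far the sample-size statement can be relied on. The study aims to show at least 95% successful treatments, so the lower limit is the part a reader will look at. The sentence suggests that 95% observed success in 50 eyes would exclude true rates below 89%. If a sounder method or some correlation between fellow eyes gives a lower limit, the study is less precise than stated.

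**Working it through.** **Inputs.** Success rate p = 0.95, n = 50 eyes, two-sided 95% level, so z = 1.96 (SAP 5, Protocol 20.3). Two eyes per subject (Protocol 4), so 50 eyes are 50/2 = 25 subjects and 100 eyes are 50 subjects. The ICC between fellow eyes is not in the documents; 0 to 1 is assumed.

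**1. Reproduce the stated figure.** Wald half-width = 1.96 × √(0.95 × 0.05 / 50) = 0.0604. Interval = (0.8896, 1.0104). Cutting the upper limit at 1 gives (89%, 100%) and 6.0%. The arithmetic is right for this method.

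Other common methods at p = 0.95, n = 50 do not give the figure:

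| Method | Interval |
|---|---|
| Wald with continuity correction | (88.0%, 102.0%), half-width 7.0 points |
| Wilson | (85.1%, 98.4%) |
| Agresti-Coull | (84.5%, 99.1%) |
| Jeffreys, 47.5/50 | (86.3%, 98.8%) |
| Exact (Clopper-Pearson), 47.5/50 | (84.85%, 99.2%) |

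95% of 50 eyes is 47.5, which is not an attainable count. It is used here only to compare methods at the rate that the plan assumes.

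**2. Coverage with independent eyes.** Sum the binomial probabilities (n = 50, p = 0.95) of the counts whose interval contains 0.95. The Wald interval misses at 50/50, where its width is zero (probability 0.95^50 = 0.0769), and at 42/50 or fewer, where its upper limit is 94.2% or less (probability 0.0032). Coverage = 1 − 0.0769 − 0.0032 = 0.920. The same sum gives 0.962 for Wilson and 0.988 for the exact interval.

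**3. Lower limit with independent eyes.** Wilson centre = (0.95 + 1.96²/100) / (1 + 1.96²/50) = 0.9179. Half-width = 1.96 / (1 + 1.96²/50) × √(0.95 × 0.05/50 + 1.96²/(4 × 50²)) = 0.0665. Interval = (0.8514, 0.9844). The lower limit is 0.8896 − 0.8514 = 0.038, or 3.8 points, below the Wald limit. Of this, 0.95 − 0.9179 = 3.2 points come from re-centring and 0.0665 − 0.0604 = 0.6 points from the wider half-width. The exact lower limit at 47.5/50 is 0.8896 − 0.8485 = 4.1 points below.

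**4. Pairing, as an assumed range.** For pairs the design effect is 1 + ICC, so the effective n is n/(1 + ICC). Putting this into the same formulas, which is an approximation, gives:

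| Eyes | ICC | Effective n | Wald half-width (points) | Wilson interval |
|---|---|---|---|---|
| 50 | 0 | 50 | 6.0 | (85.1%, 98.4%) |
| 50 | 0.5 | 33.3 | 7.4 | (81.9%, 98.8%) |
| 50 | 1 | 25 | 8.5 | (79.0%, 99.0%) |
| 100 | 0 | 100 | 4.3 | (88.8%, 97.8%) |
| 100 | 0.5 | 66.7 | 5.2 | (86.9%, 98.2%) |
| 100 | 1 | 50 | 6.04 | (85.1%, 98.4%) |

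**The case against.** The strongest reply is that nothing depends on the figure. The endpoint is an observed proportion of at least 95%, reported as a count and percentage with a list of failed eyes. There is no test and no limit to clear. A Wald half-width is a common planning approximation, the arithmetic is correct, and stopping at 100% is a natural bound. All of this stands, and it limits the point to the wording of the justification. It does not make the stated interval a 95% interval.

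A second reply is that the lower limit depends on the method. This also stands in part. The exact interval over-covers (98.8%), so some of its gap to 89% is conservatism. Most of the Wilson difference is re-centring, and the half-width itself moves only from 6.0 to 6.6 points. But Wilson is not an extreme choice: its coverage here is 96.2%, and its lower limit is still 3.8 points below the one stated.

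A third reply is that pairing may cost little. Each eye has its own Activator, no ICC is given, and at ICC 0 there is no loss. That is fair. The documents show that independence was assumed without saying so; they do not show that the assumption is wrong.

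Three stronger readings are tempting:

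- A reader might infer that the study is too small. The documents set no precision target that 50 eyes would miss, and at 100 eyes the Wald half-width is at most 6.04 points at any ICC from 0 to 1.
- A reader who takes 23 of 25 concordant subjects will find an exact lower limit of 74.0%. But 23/25 is 92% observed success, so that figure mixes a lower rate with the effect of pairing. In the same way, the exact 83.5% for 47/50 belongs to 94% success.
- A reader might infer from the 92.0% that coverage follows a simple trend with sample size. Binomial coverage oscillates with n, so the figure describes n = 50 and p = 0.95 only.

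**Conclusion.** Minor, but wrong as written. The sentence presents as a two-sided 95% interval something that covers 92.0% at its own planning values, and it gives one precision for two unequal arms. With independent eyes, the stated lower limit of 89% is about 4 points too favourable at the assumed 95% success rate. This part needs no assumption beyond the plan's own inputs and the choice of a standard score or exact interval.

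The pairing part is conditional. If fellow eyes are correlated, the 50-eye Wilson lower limit falls from 85.1% towards 79.0%, and the Wald half-width grows from 6.0 towards 8.5 points. ICC 1 is a boundary case, and the documents give no basis for choosing a value within the range.

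The consequence is confined to the stated precision. The planned primary result, the success rule and the sample size are unaffected.

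**What to change.** Keep the sample size. In Protocol 1, Protocol 20.3 and SAP 5, name the interval method, say what is assumed about fellow eyes and restate the figure, for example:

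> With 50 eyes and 95% success, the two-sided 95% Wilson interval is (85.1%, 98.4%) if fellow eyes are independent; if they are fully concordant (effective n = 25) it is (79.0%, 99.0%). With 100 eyes it is (88.8%, 97.8%) if independent and (85.1%, 98.4%) if fully concordant.

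A named exact interval would also serve. If attainable counts are used to illustrate it, give the observed rate beside each one.

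The cost is a wording change in three places, with no extra subjects and no change to the planned count and percentage. The downside for the sponsor is that the stated precision becomes less favourable: the lower limit for 50 eyes is then 85.1% or less, in place of 89%.

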APPENDIX I: TABLE LISTING

Variable	Subjects/Eyes
ENROLLMENT/PRE-TREATMENT	
Accountability/Enrollment	
Subjects by investigational site (n)	subjects
Demographics	
Demographic – Age in years (N, Mean, SD, Median, Min, Max), sex, race and ethnicity (n and %)	subjects
PRIMARY STUDY ENDPOINT	
Successful completion of LipiFlow treatment – (n, %) List of eyes with unsuccessful cases will be provided	eyes
OTHER ENDPOINTS	
Questionnaire responses of each step of LipiFlow treatment (n, %) for Yes/No or rating responses and mean and median for each rating score List of eyes with rating score of 1 or 2	eyes
Ocular surface staining at pre-treatment and treatment and the difference (N, Mean, SD, Median, Min, Max)	eyes
Meibomian glands assessment Meibomian glands secretion score at pre-treatment (if available) –(N, Mean, SD, Median, Min, Max) Proportion of utilization of meibomian gland evaluator (n,%)	eyes
Medical findings from slit lamp exam (n, %)	eyes
Ocular symptoms (n, %)	eyes
Rate of complications and adverse events (n, %)	eyes
